## Protocol summary

Protocol number	CRFB002EJP09
Title	A 12-month, phase IV, open-label, randomized, active controlled, 2-arm, multicenter study assessing the efficacy and safety of intravitreal Ranibizumab combined with Grid&Direct short pulse laser photocoagulation versus a PRN Ranibizumab monotherapy in Japanese patients with macular edema secondary to branch retinal vein occlusion (BRVO).
Brief title	Study to show a superior benefit in terms of reduction of ranibizumab injections in patients receiving ranibizumab plus laser photocoagulation combination therapy without loss of efficacy and safety.
Sponsor and Clinical Phase	Novartis Pharma K.K (Phase IV)
Investigation type	Drug, Laser photocoagulation
Study type	Interventional
Purpose and rationale	This study is designed to evaluate comparative efficacy and safety data as well as injection frequency data for ranibizumab using a pro re nata (PRN) dosing, administered with Grid&Direct short pulse laser photocoagulation versus ranibizumab monotherapy using the same dosing up to Month 12 in Japanese patients with visual impairment due to macular edema (ME) secondary to BRVO.
Primary Objective	To demonstrate that PRN regimen (PRN, according to the Japanese label of ranibizumab) of ranibizumab combined with Grid&Direct short pulse laser photocoagulation reduces the burden of frequent ranibizumab injections as compared to ranibizumab monotherapy. The primary objective will be assessed by the difference in the mean number of ranibizumab injections applied up to Month 11 between the 2 treatment arms.
Secondary Objectives	The secondary objectives of this study are as follows: 
 
• To evaluate the efficacy of each arm as assessed by Best-corrected visual acuity (BCVA)
 
• To evaluate the efficacy of each arm as assessed by center subfield thickness (CSFT)
 
• To evaluate the safety of ranibizumab monotherapy and ranibizumab combined with Grid&Direct short pulse laser photocoagulation therapy in Japanese patients as assessed by the type, frequency, and severity of ocular and non-ocular adverse events (AEs) from Baseline (Day 1) to Month 12
 

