Before anti-VEGF drugs were approved with ME secondary to BRVO, grid laser photocoagulation was the gold standard, and this excelled in maintaining VA (The Branch Vein Occlusion Study Group 1984). Therefore, medical experts expect the effect of laser photocoagulation to reduce the number of anti-VEGF injections when used in combination with anti-VEGF therapy.

A few small scale single center past studies demonstrated that laser combination therapy potentially reduced the number of anti-VEGF drug injections in BRVO (Hayashi et al. 2011, Donati et al. 2012, Farese et al. 2014, Salinas-Alaman et al. 2011, Iesato et al. 2016). Moreover, navigated laser photocoagulation (NAVILAS®) combined with ranibizumab contributed to reduce the number of ranibizumab injections in DME because of accuracy of the navigated laser system towards the pathologic area (e.g. leaking points and fluid area) (Liegl et al. 2014, Kozak et al. 2011, Neubauer et al. 2013). These results indicate that macular laser photocoagulation combined with anti-VEGF drug has a potential to reduce the number of anti-VEGF drug injections if it is used properly.

In this study, we will apply a new laser photocoagulation method, which we call Grid&Direct short pulse laser photocoagulation. Basically, the method is based on a modified Early Treatment Diabetic Retinopathy Study (ETDRS) procedure in DME. Moreover, this study will adopt a short pulse laser method to reduce the risk for retinal tissue damage (e.g. expanding atrophic creep and retinal hemorrhage). [REDACTED]

We expect the photocoagulation method used in this study will allow for a significant reduction of recurrences and therefore ranibizumab injections in BRVO patients. This study aims to show a superior benefit with regards to the reduction of ranibizumab injections in the laser photocoagulation combination arm without loss of efficacy and safety.

We expect that this phase IV study will further help to reduce the treatment burden for Japanese BRVO patients and will contribute to the advancement of BRVO treatment in Japan.

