## 1.2 Purpose

The present study will generate comparative efficacy and safety data as well as injection frequency data for 0.5 mg ranibizumab using a PRN dosing as defined in the protocol (i.e., according to the Japanese label of ranibizumab), administered with Grid&Direct short pulse laser photocoagulation versus 0.5 mg ranibizumab monotherapy using the same dosing (the current standard treatment) up to Month 12 in Japanese patients with visual impairment due to ME secondary to BRVO. [REDACTED]

[REDACTED] The results of this study will provide 1 year safety, efficacy and injection frequency data to further guide recommendations on the use of ranibizumab with or without laser photocoagulation in BRVO.

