### 2.1 Primary objective

To demonstrate that PRN regimen (PRN, according to the Japanese label of ranibizumab) with 0.5 mg ranibizumab combined with Grid&Direct short pulse laser photocoagulation reduces the burden of frequent ranibizumab injections as compared to ranibizumab monotherapy. The primary objective will be assessed by the difference in the mean number of ranibizumab injections applied up to Month 11 between the 2 treatment arms.

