### 2.2 Secondary objectives

The secondary objectives of this study are as follows:

- To evaluate the efficacy of each arms as assessed by BCVA.
- To evaluate the efficacy of each arms as assessed by center subfield thickness (CSFT).
- To evaluate the safety of ranibizumab monotherapy and ranibizumab combined with Grid&Direct short pulse laser photocoagulation therapy in Japanese patients as assessed by the type, frequency, and severity of ocular and non-ocular AEs from Baseline (Day 1) to Month 12.

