### **9.4.2 Statistical model, hypothesis, and method of analysis**

The primary analysis will be conducted at Month 12 within the FAS using observed data.

The following 1-sided hypothesis will be tested at the alpha level of 0.025:

$H_0: \mu_{\text{Ranibizumab-Laser}} - \mu_{\text{Ranibizumab-Mono}} = 0$  versus

$H_1: \mu_{\text{Ranibizumab-Laser}} - \mu_{\text{Ranibizumab-Mono}} \leq 0$

where  $\mu_{\text{Ranibizumab-Laser}}$  and  $\mu_{\text{Ranibizumab-Mono}}$  are the unknown mean values of the number of ranibizumab injections for the related treatment arms up to Month 11.

The statistical hypothesis testing of the number of ranibizumab treatments will be based on a stratified Cochran-Mantel-Haenszel (CMH) test. Stratification will be done based on categories of baseline decimal VA ( $<0.3$ , or  $\geq 0.3$ ). Difference of mean number of injections, 95% confidence interval (CI) of difference and one-sided p-value of the CMH test will be reported.

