#### **9.5.1.1 BCVA from Month 1 through Month 12**

The mean change in BCVA from Month 1 through Month 12 will be compared to Baseline (Day1) using decimal chart and ETDRS (only at Baseline (Day1), Month 6, and Month 12) between the 2 treatment arms. The analyses at each visit will be based on an analysis of variance (ANOVA) model with treatment group, and stratification factors. Stratification will be done based on categories of baseline decimal VA ( $< 0.3$ , or  $\geq 0.3$ ). The Least Squares

Means (LS Means) estimates of BCVA compared to Baseline (Day1), difference of LS Means, their 95% confidence interval (CI) and the p-value (related to the null hypothesis that difference in mean change is zero) will be reported.

The mean average change in BCVA from Month 1 through Month 12 will also be compared to baseline characteristic to the above model using decimal chart converted to be logMAR units by both the treatment arms.

To obtain the mean average BCVA change from Month 1 through Month 12, the sum of single patient's average BCVA changes will be divided by the number of patients.

The average change in BCVA will be calculated for each single patient as follows:

$$\text{Average } \Delta \text{ BCVA} = \frac{\Delta \text{ BCVA}_{M1} + \Delta \text{ BCVA}_{M2} + \dots + \Delta \text{ BCVA}_{M12}}{12}$$

Where  $\Delta \text{ BCVA}_{Mx}$  = change in BCVA from Baseline (Day1) at Month x

The analyses will be conducted within the FAS using the LOCF approach.

Endpoints related to the number and proportion of patients with BCVA letter gain or loss from Baseline (Day1) will be analyzed via stratified CMH test with stratification factors as described above.

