### 9.5.2.1 Adverse events

Adverse events will be deemed treatment emergent if the onset date is on or after the date of first study treatment (Day 1). All treatment-emergent AEs will be summarized. Any AEs recorded prior to the start of study treatment will be listed separately and together with all other AEs.

Adverse events will be presented separately by site (non-ocular, study eye, fellow eye). Adverse events will be summarized by treatment group, presenting the number and percentage of patients having an AE in each primary system organ class and having each individual AE based on the preferred term. Patients who experienced multiple AEs for a preferred term will be counted once, similarly for patients with multiple AEs per system organ class.

All information pertaining to AEs noted during the study will be listed by patient, detailing AE (e.g., verbatim given by the investigator as well as the system organ class and preferred term according to MedDRA), date of starting and ending, causality, severity, relationship to the study drug or procedure, and eye (for ocular events). The AE onset will also be shown relative (in number of days) to the day of (first) initial study treatment (ranibizumab injection or laser photocoagulation as applicable) and relative (in number of days) to the Day 1.

Summary tables will also be presented and described for subsets of AEs, e.g. events potentially related to VEGF-inhibition. Adverse events which are part of the Risk Management plan (RMP) will be listed based on the latest RMP version available at the time of DBL.

The following AE listings will be provided:

- Any AE recorded before Day 1.
- Any treatment-emergent AEs with the exception of ocular AEs of the fellow untreated eye starting on or after first treatment with ranibizumab within this eye.
- Any treatment-emergent AEs of the fellow treated eye starting on or after the first treatment with ranibizumab within this eye.
- Any AEs for patients who (bilateral patients) received 3 or more injections of study drug within a  $30 \pm 7$  days period starting on or after the third injection within the  $30 \pm 7$  days period.

Deaths, SAEs, and AEs leading to discontinuation of study treatment will be listed separately and, if appropriate, summarized by primary system organ class and preferred term.

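### The brief title and Section 1.1 promise fewer injections with no loss of efficacy or safety, but the design can demonstrate only the injection part; vision, retinal thickness and safety are estimated or described, without a margin

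*Protocol*

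**What the plan says.** Two places state the aim with a no-loss qualifier. The brief title in the Protocol summary describes a study to show a benefit in patients receiving "ranibizumab plus laser photocoagulation combination therapy without loss of efficacy and safety". Section 1.1 says the study aims to show a superior benefit in "reduction of ranibizumab injections in the laser photocoagulation combination arm without loss of efficacy and safety".

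The operative sections are narrower:

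- **Section 1.2 (Purpose):** "The present study will generate comparative efficacy and safety data as well as injection frequency data".
- **Section 2.1 (primary objective):** "The primary objective will be assessed by the difference in the mean number of ranibizumab injections applied up to Month 11".
- **Section 2.2 (secondary objectives):** "To evaluate the efficacy of each arms as assessed by BCVA", with parallel wording for CSFT and for safety.
- **Section 9.4.2:** "The following 1-sided hypothesis will be tested at the alpha level of 0.025". The hypothesis concerns the mean number of injections.
- **Section 9.8:** the sample size assumes a difference of 2 injections and an SD of 2.32. No other endpoint enters it.
- **Section 9.5.1.1:** BCVA change is analysed by ANOVA with treatment and baseline-VA stratum. LS means and their difference are given, and "their 95% confidence interval (CI) and the p-value (related to the null hypothesis that difference in mean change is zero) will be reported". Letter gain and loss proportions, including the proportion losing fewer than 15 letters (Section 9.5.1), are compared by stratified CMH test.
- **Section 9.5.1.2:** CSFT is analysed in the same way as BCVA.
- **Sections 9.5.2.1 and 9.5.2.4:** "Adverse events will be summarized by treatment group, presenting the number and percentage of patients having an AE in each primary system organ class". Ocular assessments are summarised descriptively by time point and arm.

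No section shown gives a non-inferiority or equivalence margin, or says what interval would count as no loss.

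**The concern.** Fewer injections help patients only if vision is kept. Section 1.1 itself gives the need as reducing injections while maintaining efficacy, Section 3.6 presents a possible similar efficacy with fewer injections as the benefit of joining, and Section 1.2 expects the results to guide recommendations on use with or without laser. The no-loss half of the aim is therefore the half on which a reader will rely.

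Showing that nothing was lost means ruling out a loss of some stated size. The planned BCVA and CSFT p-values test zero difference, and failing to reject that null does not rule out any particular loss. At stake is the conclusion the trial may draw: a significant reduction in injections next to a non-significant BCVA difference could be reported as meeting the whole stated aim, although only the first half had been tested in a way that could establish it.

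**Working it through.** **1. What the sample size covers.** Inputs from Section 9.8: difference 2 injections, SD 2.32, one-sided alpha 0.025, power 80%, Wilcoxon-Mann-Whitney test.

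- Noether's formula with a normal shift: p = Φ(2 / (2.32 × √2)) = 0.729.
- Total N = (1.960 + 0.842)² / (12 × 0.25 × (0.729 − 0.5)²) = 49.9, that is 25 per arm.
- With 10% dropout: 25 / 0.9 = 27.8, so 28 per arm and 56 in total.

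The stated figures reproduce, and they rest on injections alone.

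**2. Aim against design.**

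| Part of the stated aim | Objective | Hypothesis able to demonstrate it | Sized | Planned output |
|---|---|---|---|---|
| Fewer injections | Section 2.1, to demonstrate | Yes, one-sided 0.025 | Yes | Difference, 95% CI, p-value |
| No loss of efficacy: BCVA, CSFT | Section 2.2, to evaluate | No; zero-difference null, no margin | No | LS-mean difference, 95% CI, nominal p-value |
| No loss of efficacy: letter gain and loss | Section 2.2, to evaluate | No; no margin | No | Stratified CMH test |
| No loss of safety | Section 2.2, to evaluate | No | No | Summaries by arm |

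**3. Illustration for BCVA.** The protocol gives no SD of BCVA change and no margin, so both are assumed here: SD 10, 12, 15 and 18 ETDRS letters, and a 5- or 10-letter loss. The model is a two-sample t comparison at Month 12 with 28 per arm, df = 54, t(0.975, 54) = 2.005.

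- Half-width = 2.005 × SD × √(2/28). For SD 10: 2.005 × 2.673 = 5.36 letters.
- Probability that a true 5-letter loss is non-significant: noncentral t with noncentrality 5 / (SD × √(2/28)).
- Probability that the 95% CI excludes a given loss when the arms are truly equal: same distribution, with noncentrality equal to that loss over the standard error.

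| Assumed SD (letters) | 10 | 12 | 15 | 18 |
|---|---|---|---|---|
| 95% CI half-width | 5.36 | 6.43 | 8.04 | 9.65 |
| P(non-significant, true 5-letter loss) | 0.549 | 0.666 | 0.768 | 0.825 |
| P(CI excludes 5-letter loss, equal arms) | 0.451 | 0.334 | 0.231 | 0.174 |
| P(CI excludes 10-letter loss, equal arms) | 0.957 | 0.865 | 0.688 | 0.533 |

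The last two rows show how far the answer depends on a margin that the protocol does not set. The stratum term costs one degree of freedom and changes the half-width by less than 0.01 letters; any variance it explains would narrow the interval and is not counted. The Month 1 to 12 average, which is in logMAR, is not modelled. The Amendment 2 rationale reports 59 patients already randomised with enrolment continuing; at 59 the SD 10 half-width would be about 5.2 instead of 5.4 letters, so the picture does not change.

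**The case against.** The strongest reply is that no operative section is wrong. The no-loss phrase stands only in the brief title and the background, where it trails a statement about injections. Purpose, objectives, hypothesis and sample size do not repeat it, and Section 3.6 is hedged. This stands. It makes the point a mismatch between stated aim and design, but it does not remove it: both places say what the study is meant to show.

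Second, Section 9.5.1.1 already plans the LS-mean difference with its 95% CI, names no decision statistic, and adds CMH tests on letter gain and loss, which bear directly on loss of vision. This also stands, and it is why the repair is cheap. These analyses estimate or compare; none states how large a loss would have to be excluded.

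Third, the SAP is not shown, and Section 9.5.1 leaves further analyses to it. A margin there would still leave the protocol's stated aim without a matching objective or sizing.

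Fourth, shared re-treatment criteria (Section 5.5.4.2) and a masked vision examiner (Section 5.4) protect the comparison. They limit bias, but they do not define or test absence of loss.

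Two stronger readings are tempting. A reader might infer that the sponsor intends to treat a non-significant BCVA p-value as proof of preserved vision; the protocol does not say so. A reader might also infer that the trial is too small; with no margin or BCVA SD in the protocol, and objectives that only evaluate BCVA, the documents do not support that.

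**Conclusion.** The point holds as a mismatch between the stated aim and the design. The protocol can demonstrate a reduction in injections. It can estimate differences in BCVA and CSFT, compare letter gain and loss, and describe safety, but it cannot demonstrate that nothing was lost in efficacy or safety.

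The illustrated size is a BCVA interval of about ±5 to ±10 letters, with a true 5-letter loss going undetected by the zero-difference test in about 55% to 82% of trials. It rests on assumed SDs of 10 to 18 letters, 28 per arm and a single-visit Month 12 comparison. The mismatch itself follows from the text and needs none of these assumptions.

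This is not an error in the primary analysis, whose sample size reproduces. The change is worth making because it governs what the trial may conclude and costs almost nothing.

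**What to change.** 1. In the brief title and in Section 1.1, replace the no-loss wording with text that matches Section 2, for example: *and to evaluate efficacy (BCVA, CSFT) and safety in each arm*. This keeps safety in view as a secondary objective.
2. In Section 9.5.1.1, add: *The between-arm difference in BCVA change (combination minus monotherapy) at Month 12 and for the Month 1 to 12 average will be interpreted from its 95% CI. A non-significant p-value will not be taken as evidence of no loss of vision.* Note beside it that a loss is a negative difference in letters and a positive one in logMAR.
3. Only if the sponsor wants to keep the efficacy claim: fix a justified margin by amendment before any BCVA data are summarised by arm, together with the BCVA endpoint and time point, the analysis sets and the missing-data handling. Set this late in an open-label trial, a margin would carry limited weight, and the claim may not be reachable at this size. It would not support a no-loss claim for safety.

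Cost of items 1 and 2: wording in one amendment, with no new data, patients or analyses, since the confidence interval is already planned. The downside is a more cautious claim.

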#### **9.5.1.2 Central subfield thickness from Month 1 through Month 12**

The mean change in investigator-assessed CSFT from Month 1 through Month 12 will be compared to Baseline (Day1) by the treatment arms. The analyses at each visit will be based on an analysis of variance (ANOVA) model as analogous to BCVA.

The mean average change in investigator-assessed CSFT from Month 1 through Month 12 will also be compared to Baseline (Day1) analogous to the above model by both the treatment arms.

The analyses will be conducted within the FAS using the LOCF approach.

#### **9.5.1.3 Handling of missing values/censoring/discontinuations**

For the secondary efficacy variables (BCVA, CSFT etc.), the analysis will follow a LOCF approach with the specification that missing values will be replaced by the last post baseline observation before the missing time point.

#### **9.5.1.4 Sensitivity analyses**

For sensitivity purposes, the secondary efficacy analysis may be repeated for the PPS population using as observed and LOCF approach. Any major discrepancies in the results across analyses will be investigated as necessary.

### **9.5.2 Safety variables**

Safety parameters will be AEs, ophthalmic examinations, IOP, vital signs, and laboratory results.

### 9.5.2.1 Adverse events

Adverse events will be deemed treatment emergent if the onset date is on or after the date of first study treatment (Day 1). All treatment-emergent AEs will be summarized. Any AEs recorded prior to the start of study treatment will be listed separately and together with all other AEs.

Adverse events will be presented separately by site (non-ocular, study eye, fellow eye). Adverse events will be summarized by treatment group, presenting the number and percentage of patients having an AE in each primary system organ class and having each individual AE based on the preferred term. Patients who experienced multiple AEs for a preferred term will be counted once, similarly for patients with multiple AEs per system organ class.

All information pertaining to AEs noted during the study will be listed by patient, detailing AE (e.g., verbatim given by the investigator as well as the system organ class and preferred term according to MedDRA), date of starting and ending, causality, severity, relationship to the study drug or procedure, and eye (for ocular events). The AE onset will also be shown relative (in number of days) to the day of (first) initial study treatment (ranibizumab injection or laser photocoagulation as applicable) and relative (in number of days) to the Day 1.

Summary tables will also be presented and described for subsets of AEs, e.g. events potentially related to VEGF-inhibition. Adverse events which are part of the Risk Management plan (RMP) will be listed based on the latest RMP version available at the time of DBL.

The following AE listings will be provided:

- Any AE recorded before Day 1.
- Any treatment-emergent AEs with the exception of ocular AEs of the fellow untreated eye starting on or after first treatment with ranibizumab within this eye.
- Any treatment-emergent AEs of the fellow treated eye starting on or after the first treatment with ranibizumab within this eye.
- Any AEs for patients who (bilateral patients) received 3 or more injections of study drug within a  $30 \pm 7$  days period starting on or after the third injection within the  $30 \pm 7$  days period.

Deaths, SAEs, and AEs leading to discontinuation of study treatment will be listed separately and, if appropriate, summarized by primary system organ class and preferred term.

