### Screening Period: Day -30 to Day -1

Screening (Visit 1) to occur between Day -30 and Day -1 where screening assessments will be done between Day -30 and Day -4 after signing the informed consent form to check the eligibility for the study and administration of pre-ranibizumab treatment antimicrobials will occur between Day -3 to Day -1.

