## 6.1 Information to be collected on screening failures

Patients who are screened but determined not eligible for treatment are considered screening failures. The reason for this will be documented on the Screening Log. In addition, for all screening failures, the Screening Visit date, demography eCRF, Informed Consent eCRF, inclusion/exclusion, reason of screen failure on Screening Disposition, Demography and SAE data will be collected.

Adverse events that are not SAEs will be followed by the investigator and collected only in the source data. For all patients who have signed informed consent and are entered into the next period of the study will have all AEs occurring after informed consent is signed recorded on the AE eCRF.

Investigators will have the discretion to record abnormal test findings on the medical history eCRF whenever in their judgment, the test abnormality occurred prior to the informed consent signature.

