### **7 Safety monitoring**

#### **7.1 Adverse events**

An AE is any untoward medical occurrence (e.g., any unfavorable and unintended sign (including abnormal laboratory findings), symptom or disease) in a subject or clinical investigation subject *after providing written informed consent* for participation in the study until the end of study visit. Therefore, an AE may or may not be temporally or causally associated with the use of a medicinal (investigational) product.

In addition, all reports of intentional misuse and abuse of the product are also considered an AE irrespective if a clinical event has occurred.

The occurrence of AEs must be sought by non-directive questioning of the patient at each visit during the study. Adverse events also may be detected when they are volunteered by the patient during or between visits or through physical examination findings, laboratory test findings, or other assessments. Adverse events will be collected from signing of ICF through the end of trial.

Abnormal laboratory values or test results constitute AEs only if they fulfill at least one of the following criteria:

- they induce clinical signs or symptoms,
- they are considered clinically significant,
- they require therapy.

Clinically significant abnormal laboratory values or test results must be identified through a review of values outside of normal ranges/clinically notable ranges, significant changes from Baseline (Day1) or the previous visit, or values which are considered to be non-typical in patient with underlying disease. Investigators have the responsibility for managing the safety of individual patient and identifying AEs.

Adverse events must be recorded in the AEs eCRF under the signs, symptoms or diagnosis associated with them, accompanied by the following information:

1. the severity grade. If CTCAE grading does not exist for an AE, use 1=mild, 2=moderate, 3=severe, 4=life threatening. CTCAE Grade 5 (death) is not used, but is collected in other eCRFs (Study Completion).
2. site (non-ocular, left eye, right eye, both eyes).

3. its relationship to the ocular injection/study drug(s) (Yes/No).
4. its duration (start and end dates or if continuing at final exam).
5. whether it constitutes an SAE (see [Section 7.2.1](#) for definition of SAE).

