All AEs should be treated appropriately. Treatment may include one or more of the following: no action taken (i.e. further observation only); study drug dosage adjusted/temporarily interrupted; study drug permanently discontinued due to this AE; concomitant medication given; non-drug therapy given; patient hospitalized/patient's hospitalization prolonged. The action taken to treat the AE should be recorded on the Adverse Event eCRF.

Once an AE is detected, it should be followed until its resolution or until it is judged to be permanent, and assessment should be made at each visit (or more frequently, if necessary) of any changes in severity, the suspected relationship to the study drug, the interventions required to treat it, and the outcome.

Information about common side effects already known about the investigational drug can be found in the package insert. This information will be included in the patient informed consent and should be discussed with the patient during the study as needed. Any new information regarding the safety profile of the medicinal product that is identified between package insert updates will be communicated as appropriate, for example, via an Investigator Notification or an Aggregate Safety Finding. New information might require an update to the informed consent and has then to be discussed with the patient.

The investigator must also instruct each patient to report any new AE (beyond the protocol observation period) that the patient, or the patient's personal physician, believes might reasonably be related to study treatment. This information must be recorded in the investigator's source documents; however, if the AE meets the criteria of an SAE, it must be reported to Novartis.

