## **7.2 Serious adverse events**

### **7.2.1 Definition of SAE**

An SAE is defined as any AE [appearance of (or worsening of any pre-existing)] undesirable sign(s), symptom(s) or medical condition(s) which meets any one of the following criteria:

- is fatal or life-threatening
- results in persistent or significant disability/incapacity
- constitutes a congenital anomaly/birth defect
- requires inpatient hospitalization or prolongation of existing hospitalization, unless hospitalization is for:
  - routine treatment or monitoring of the studied indication, not associated with any deterioration in condition (specify what this includes)
  - elective or pre-planned treatment for a pre-existing condition that is unrelated to the indication under study and has not worsened since signing the informed consent
  - treatment on an emergency outpatient basis for an event not fulfilling any of the definitions of a SAE given above and not resulting in hospital admission

- social reasons and respite care in the absence of any deterioration in the patient's general condition
- is medically significant, e.g. defined as an event that jeopardizes the patient or may require medical or surgical intervention to prevent one of the outcomes listed above.

Unlike routine safety assessments, SAEs are monitored continuously and have special reporting requirements; see [Section 7.2.2](#).

All malignant neoplasms will be assessed as serious under “medically significant” if other seriousness criteria are not met.

Life-threatening in the context of a SAE refers to a reaction in which the patient was at risk of death at the time of the reaction; it does not refer to a reaction that hypothetically might have caused death if it were more severe (please refer to Annex IV, ICH-E2D Guideline).

Medical and scientific judgment should be exercised in deciding whether other situations should be considered serious reactions, such as important medical events that might not be immediately life threatening or result in death or hospitalization but might jeopardize the patient or might require intervention to prevent one of the other outcomes listed above. Examples of such events are intensive treatment in an emergency room or at home for allergic bronchospasm, blood dyscrasias or convulsions that do not result in hospitalization or development of dependency or abuse (please refer to Annex IV, ICH-E2D Guideline).

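### Treatment emergence rests on onset date alone, so a non-serious adverse event that starts in screening and worsens after first treatment can be missing from the treatment-emergent summaries

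*Protocol*

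**What the plan says.** Protocol Section 9.5.2.1 defines the class by one date comparison: "Adverse events will be deemed treatment emergent if the onset date is on or after the date of first study treatment (Day 1". It then assigns outputs. For the class so defined, "All treatment-emergent AEs will be summarized". For the rest, "Any AEs recorded prior to the start of study treatment will be listed separately and together with all other AEs".

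Collection begins well before Day 1. Section 7.1 states that "Adverse events will be collected from signing of ICF through the end of trial". Section 6.1 adds that patients who go on past screening "will have all AEs occurring after informed consent is signed recorded on the AE eCRF". Section 3.1 sets the window: "Screening (Visit 1) to occur between Day -30 and Day -1".

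On events that change over time, Section 7.1 requires that a detected event be followed until it resolves or is judged permanent, and that "assessment should be made at each visit (or more frequently, if necessary) of any changes in severity". The items to be recorded for each event include a severity grade and start and end dates. A date of worsening is not among them. Section 7.2.1 mentions worsening in its definition of a serious event: "appearance of (or worsening of any pre-existing" sign, symptom or condition.

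**The concern.** The secondary safety objective in Section 2.2 covers the kind, frequency and severity of adverse events from Day 1 to Month 12. An increase in severity after Day 1 lies inside that period and concerns one of the named attributes. A rule that looks only at the first onset date ignores it.

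At stake is the completeness of the by-arm tables that serve this objective. A second consequence is uneven counting. If the protocol does not say whether a worsening opens a new record, two sites can enter the same clinical course differently, and only one of the two entries will be counted as treatment emergent.

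**Working it through.** There is no stated figure to reproduce; the check is to apply the rule as written.

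**1. Can an event with onset before Day 1 be in the database?** Yes. Collection runs from consent (Sections 6.1 and 7.1), and screening may begin on Day -30 (Section 3.1).

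**2. What happens to its onset date if it worsens?** Section 7.1 treats a change in severity as follow-up of the detected event. No section tells the site to close the record and open another, and no section forbids it.

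**3. Apply the test to one course entered in two ways.** A mild event starts on Day -10 and becomes severe after the Day 1 injection.

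| Entry | Onset date tested | On or after Day 1? | Result |
|---|---|---|---|
| One record, severity updated | Day -10 | No | Listings only |
| New record at the worsening | After the Day 1 injection | Yes | Treatment emergent, summarized |

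The result depends on an entry convention that the protocol does not set.

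**4. Which outputs would still show the first entry?** Section 9.5.2.1 provides a by-patient listing of all events with dates and severity, and a listing of events recorded before Day 1. Deaths, serious events and events leading to discontinuation of study treatment are listed and, where appropriate, summarized, with no stated restriction to treatment-emergent events. The gap is therefore confined to events that are non-serious and do not stop treatment. The sentence describing the by-arm table does not repeat the treatment-emergent qualifier. But the section opens by sending treatment-emergent events to summaries and pre-treatment events to listings, and that is the natural reading of what follows.

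**5. Size.** Section 9.8 plans at least 28 patients per arm (56 in total). One omitted patient changes an arm's incidence by 1/28 = 0.036, or 3.6 percentage points.

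The protocol gives no rate for events ongoing at Day 1 or for their worsening. As an assumption only, take 5% to 15% of patients with an event ongoing at Day 1, and 10% to 30% of those worsening:

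- low: 56 × 0.05 × 0.10 = 0.28 patients
- high: 56 × 0.15 × 0.30 = 2.52 patients

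That is between none and about three patients across both arms. The range reflects the assumed rates and is not evidence of how many there will be.

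**The case against.** The best counter-argument is that the onset rule already works if a worsening is entered as a new event. The bracketed words in Section 7.2.1 can be read as explaining what an adverse event is, so that worsening of a pre-existing sign is itself an event with its own onset. This reading is possible. However, the words stand in the definition of a serious event, the general definition in Section 7.1 has no such wording, and nothing requires sites to record events that way. The reading shows that the gap may close in practice, not that the protocol closes it.

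A second argument is that such detail belongs in the statistical analysis plan, to which Section 9 refers for further details. Record-entry conventions may well sit there or in the form-completion guide. But Section 9.5.2.1 does not leave the definition open: it states it, and a plan that followed it faithfully would carry the gap forward.

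A third argument is that little is lost, and this largely stands. Events that are serious or that stop treatment have their own outputs, and everything is listed. Intraocular pressure, other ocular assessments, vital signs and laboratory values are summarized separately. Conditions present before consent may be held as medical history, and if their worsening is entered as a new event after Day 1 it already counts.

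A reader might also think of a reaction to the antimicrobial drops given on Day -3 to Day -1 as the typical case. Exclusion criterion 9 in Section 4.2 bars active ocular or periocular inflammation in either eye at Baseline, so most such reactions would prevent randomization. The point does not rest on that example.

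**Conclusion.** The point holds in a limited form. As written, the rule allows a non-serious adverse event that begins between consent and Day 1, worsens after first treatment and does not lead to discontinuation to be missing from the treatment-emergent summaries in either arm. This assumes that the worsening stays on the existing record, which fits Section 7.1 best but is not expressly required. The number of patients cannot be derived from the protocol and is probably very small; each would be worth 3.6 percentage points in an arm of 28.

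A reader might infer that the rule flatters the combination arm, because laser is study treatment only in Arm 2 and laser-related worsening of a screening event could be lost only there. The documents do not support that conclusion. The rule is identical in both arms, both receive ranibizumab, and injection-related worsening can be lost in either. On the trial's own hypothesis Arm 1 receives more injections, so losses there could match or exceed those from laser. For an event that began after Day 1 but before the first laser session, the onset rule is met and the event is counted. No direction of bias between arms is shown.

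The primary analysis is unaffected.

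**What to change.** In Section 9.5.2.1, extend the definition with the clause: *or if the event started before Day 1 and increased in severity or became serious on or after that date*. State that such events are counted at the worsened severity.

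State also how the worsening is dated. If the adverse event form does not date changes in severity, have a worsening on or after Day 1 entered as a new record with its own onset date. Because Section 9.5.2.1 counts a patient once per preferred term, and pre-treatment records stay in the listings, a second record would not inflate the summaries.

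The cost is one clause, a small change in derivation and one line of instruction to sites, which already assess severity at each visit. Reported incidence may rise slightly.
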